Life Events Checklist for DSM-5 (LEC-5), *This form will be asked once at any upcoming timepoint (including monthly assessments)		*	*	*	17
Global Mindfulness				X	13
EHR Outcomes					
Opioid prescriptions and other prescriptions for pain, CT/MRIs of lumbar-sacral spine, injections of lumbar-sacral spine, ED/urgent care visits for LBP, Surgeries of lumbar spine, hospitalizations for LBP, PCP visits for LBP, physical therapy referrals for LBP	X		X		X
Core HEAL Pain Data Measures					
PROMIS Physical Function (questions 1-4 same as in PROMIS 29 questions 1-4)	X		X		2 additional questions
PROMIS Sleep (questions 1-4 same as in PROMIS 29 questions 17-20)	X		X		2 additional questions
Sleep Disturbance	X		X		2
Depression PHQ-2	X		X		2
Anxiety GAD-2	X		X		2

*Primary Timepoint **Primary outcome.

Pain impact is defined as Pain intensity, pain interference and functional status calculated from 9 items of the PROMIS-29. PROMIS: patient reported outcomes measurement information system.

Yellow Highlight=Core HEAL Measures incorporating into OPTIMUM outcomes.

Additional Baseline Variables: We will assess age, sex, race, ethnicity, and socioeconomic status, involvement in workers' compensation, work status, previous treatment including nonpharmacological therapies, and marital and educational status. Biomedical factors will include: a) comorbidity: data on comorbidity will be gathered using the Charlson Co-Morbidity Index T1;⁶⁰ b) pain medications (regularly scheduled and as-needed) at T1-T4 and will be categorized into sub-classes: i) salicylates (aspirin > 1200 mg/day, salsalate); ii) non-aspirin, non-COX2 selective NSAIDs; ii) COX2 selective NSAIDs; iv) acetaminophen; v) opioids; vi) skeletal muscle relaxants; vii) adjunctive agents (e.g., corticosteroids, capsaicin, Neurontin); and c) antidepressants and antianxiety medications. Regularly scheduled opioid analgesics will be converted to daily oral morphine equivalents.⁶¹

Randomization

To ensure balance between groups, we will use permuted block randomization with block size of 4 or 6, in a 1:1 ratio, stratified by clinic and sex. Participants will be randomized after completion of baseline measures.

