9.2 Sample Size and Randomization

Our target sample size of 450 patients with cLBP \geq 18 years of age will be individually randomized either to an

- 1) 8-week mindfulness clinical pain program (n=225) + PCP Usual Care or
- 2) PCP Usual Care (n=225).

Randomization and Treatment Assignment Procedure

To ensure balance between groups, we will use permuted block randomization with block size of 4 or 6, in a 1:1 ratio, stratified by clinic and sex. Co-I [name] (lead statistician) will generate the randomization sequence using SAS version 9.4, which will be implemented in the database so that the group allocation will be revealed only when each patient consents and is randomized. The randomization schedule will be created prior to enrollment and the study statistician will remain blinded to treatment assignment. We chose to randomize at the patient level rather than at the cluster level (provider or clinic) based on our responses to design choice clarification questions recommended by the NIH Collaboratory: 1) the impact of the pain program in the real-world setting is primarily at the level of the individual patient, as OPTIMUM is delivered to the patient and not the provider, for example, we are not studying implementation of provider treatment guidelines, which could result in contamination if randomized at the patient level 2) randomization at the patient level will not interfere with usual care for the patient with cLBP 3) contamination, if it occurs, will be minor. Contamination cannot be completely eliminated in either cluster or traditional RCT designs and we expect either design has a small risk of staff or patients discussing study details (“comparing notes”) as medical care is delivered in teams and patients go to a variety of clinics depending on appointments with specialists. Additionally, randomization at the patient level allows for efficient use of limited resources (reducing cost and time to completion of the study) while still including a large sample size and maintaining scientific rigor.

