We will examine opioid prescription for cLBP in two ways. First, we will examine the dose of opioids as morphine dose equivalent (continuous outcome) for those subjects with an opioid prescription at baseline. The analytic approach will mirror the mixed models described for Hypothesis 1 to compare group doses over time and in relation to baseline. Next we will use a binary outcome which is yes/no for opioid prescription (any) for each patient at each time point. Analytic methods will again mirror methods for Hypothesis 1 now using a logistic mixed effects model.

Aim 2. To evaluate use of healthcare resources by patients.

Hypothesis: patients in OPTIMUM will have fewer emergency department visits, fewer hospitalizations, fewer imaging (CT/MRI), and fewer procedures (injections, surgery) than PCP usual care.

Healthcare utilization over 6- and 12-months (prescriptions of opioids, injections, surgery, CT/MRI, ED visits, hospitalizations) are mostly in the form of counts. We will fit a series of GEE models with each outcome as the dependent variable, a negative binomial distribution to account for over dispersion, a log link, exposed time period as an offset, intervention arm (OPTIMUM/Usual Care) as the independent factor of interest, and an exchangeable correlation structure for clustering. Alternative correlation structures will be examined via the QIC statistic. Intervention arm incident rate ratios and their significance will constitute the test of the hypothesis.

Aim 3. To evaluate PCP and practice site use of, satisfaction with, and integration of OPTIMUM.

PCP satisfaction with the pain program will be summarized using descriptive statistics and histograms. We will also investigate if these measures are different depending on the demographic characteristics of the PCPs, such as gender, age, race, ethnicity, clinic location, and years since training, or the outcome of the patients using t-test, chi-square test, Pearson or Spearman correlation tests. Number of 8-week programs delivered at each clinic will also be summarized with descriptive statistics. Adoption of EHR tools and OPTIMUM after study completion will be described.

Planned Analysis & Power Assessment

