The table below is of power calculations for the Optimum study using the PEG as the primary outcome. An ICC estimate of 0.053 was used, which came from [name] pragmatic clinical trial funded by NINDS which used the PEG. The other assumptions are $\alpha = 0.05$, SD of change = 2.5 and 20% attrition. As the table illustrates, with a total sample size of 450, with an average of 10 subjects per cluster, we have close to 90% power to detect a 1-unit difference in the PEG between groups. The table also illustrates calculations for a range of power and effect sizes.

ICC = 0.053

Obs	power	meandiff	SD	clustsize	final_npergroup
1	0.80	1.0	2.5	10	184.625
2	0.85	1.0	2.5	10	210.473
3	0.90	1.0	2.5	10	245.551
4	0.80	1.5	2.5	10	83.081
5	0.85	1.5	2.5	10	94.159
6	0.90	1.5	2.5	10	110.775
7	0.80	2.0	2.5	10	48.003
8	0.85	2.0	2.5	10	55.388
9	0.90	2.0	2.5	10	62.773
10	0.80	2.5	2.5	10	31.386
11	0.85	2.5	2.5	10	35.079
12	0.90	2.5	2.5	10	42.464
13	0.80	3.0	2.5	10	22.155

Obs	power	meandiff	SD	clustsize	final_npergroup
14	0.85	3.0	2.5	10	25.848
15	0.90	3.0	2.5	10	29.540

Missing Data Considerations:

We anticipate 20% attrition at the 8-week time point. We chose a higher attrition rate than in our previous work as we anticipate more attrition in the PCT as patients will not have the “high touch” of participants in the RCTs.^{5, 26, 28} Our sample size analyses have accounted for this amount of missing data. We will compare baseline characteristics between patients with the assessment immediately following the 8-week program to those without in order to assess potential bias in study completion. We will also try to obtain reasons for study drop out so that we can assess the missing data mechanism (missing completely at random (MCAR), missing at random (MAR), non-ignorable missingness). At a single time point, we will conduct sensitivity analyses assigning poor scores and good scores for missing values differentially by treatment assignment to evaluate the impact on our study results.

The mixed models proposed for analysis are robust to missing data under MCAR and MAR missing data mechanisms. If the amount missing data differs between treatment groups or appears to be non-ignorably missing, we will conduct sensitivity analyses with imputed data based on varying assumptions (ignorable vs. non-ignorable missingness).

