10.2 Data Management

EHR Data: Consenting and eligible participants will provide contact information containing protected health information (PHI) to each HCS’s research staff. PHI will be stored separately from clinical data in a password protected electronic file and will be used to link and extract clinical data from each center’s EHR on a bi-weekly basis. Limited use datasets will be created

at each HCS and will contain a unique study identifier and clinical data including date of birth and visit dates; name, address, social security number and medical record number information will be removed. Limited use datasets will be transferred to the central data repository housed at Boston University Biostatistics and Epidemiology Data Analytics Center (BEDAC). The BEDAC is supported by the Boston University Medical Campus (BUMC) Information Systems and Technology group (IS&T). Data will reside on virtual machines stored inside the BUMC IS&T premium secure environment. Under IS&T, project database access is configured to require encrypted connections, databases are encrypted at rest (AES-256), and all actions to the database are logged. Database transfer will be electronically encrypted via IPsec tunnel or secure socket layering (SSL) encryption technology so that only the intended recipient can decode the data. Applications and databases will be protected by network firewalls that restrict access to designated users and hosts. Restriction and permissions to update the database and to share the database will be controlled by the BEDAC based on staff user role. The BEDAC data manager will develop data transfer specifications and work with each HCS to obtain data through the secure BEDAC portal. The limited use EHR data will be cleaned, aggregated and merged with study data for subsequent analysis.

Missing data: We do not expect substantial missing data due to it being directly entered into the electronic data collection system, which we have used previously. This system has many safeguards such as prohibiting closure of a page if a question has not been answered or the answer is out of range. For instruments with several questions we will use the approach recommended by their authors for calculating total scores and composites when values for an item are missing.

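### Aim 2 count models do not pre-specify the baseline utilisation count that Table 2 schedules at T1; the cost is precision, mainly for commoner, persistent use

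*Combined protocol and SAP*

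**What the plan says.** The EHR block of Table 2 (Section 6.2.2) begins "Opioid prescriptions and other prescriptions for pain, CT/MRIs of lumbar-sacral spine, injections of lumbar-sacral spine" and continues with emergency or urgent care visits, lumbar surgery, hospitalisations, primary care visits and physical therapy referrals. The later columns of that row are broken in the text available, but its first mark falls under T1. No look-back period is given for the T1 value in the text available.

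Section 9.6, Aim 2, analyses utilisation over 6 and 12 months, mostly as counts. Each outcome has its own GEE model with a negative binomial distribution, a log link, exposure time as an offset, and "intervention arm (OPTIMUM/Usual Care) as the independent factor of interest, and an exchangeable correlation structure for clustering". The test is the arm rate ratio. No baseline count, time term or arm-by-time contrast appears.

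Two other parts of Section 9.6 bear on this. The data evaluation text, which stands ahead of all the aims, says that a baseline variable will be adjusted for if the arms differ on it, either at p < 0.2 or clinically. Under Aim 1, the T1 PEG is part of the modelled outcome series, and the Hypothesis 3 opioid-dose model compares doses with baseline.

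**The concern.** A patient's earlier use of a service usually predicts later use of the same service. A baseline count is therefore a natural covariate, and this trial already plans to collect one. For visits, imaging and procedures it is the only baseline count scheduled, because the self-report utilisation form in Table 2 is not marked at T1.

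As written, the count enters a model only through the imbalance rule. That rule selects covariates by chance difference between arms, not by how well they predict the outcome. It can also give different covariate sets across the Aim 2 models, chosen after the data are seen. Nor can it be applied consistently until the T1 count has a defined window. At stake is the width of the intervals for the Aim 2 rate ratios, for which the plan gives no power calculation.

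**Working it through.** **1. The plan's own calculation.** The only sizing in Section 9.6 is for the PEG: "An ICC estimate of 0.053 was used", with "SD of change = 2.5 and 20% attrition" and 10 patients per class. The design effect is 1 + 9 × 0.053 = 1.477. Two-sample t-test sizes for a 1-unit difference are 100, 114 and 133 per arm at 80%, 85% and 90% power. Multiplied by 1.477 and divided by 0.80, these give 184.625, 210.47 and 245.55, which match the table. At 225 per arm the effective size is 225 × 0.80 / 1.477 = 121.9 and power is 87.5%, in line with the statement of nearly 90%. None of this covers the Aim 2 counts.

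**2. How often the imbalance rule would fire by chance.** Aim 2 lists six outcomes. If their baseline tests were independent and each had a 20% chance of p < 0.2 under correct randomisation, at least one would be flagged with probability 1 − 0.8⁶ = 0.74. Correlated or sparse counts would change this figure.

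**3. What the baseline count is worth.** The documents give no event rate, dispersion or persistence, so these are assumed over a range:
- μ = events per patient in the follow-up window
- k = negative binomial dispersion, 1 to 4
- ρ = correlation between a patient's underlying rate before and after randomisation (1 = fully persistent, 0.5 = half persistent)
- n = 225 × 0.80 = 180 per arm, borrowing the PEG attrition; n cancels in the percentage narrowing
- look-back and follow-up windows of equal length; class clustering left out

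Unadjusted: Var(log rate ratio) ≈ (2/n)(1/μ + k).

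Adjusted: replace k by k[1 − ρ² kμ/(1 + kμ)].

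Example, commoner outcome (μ = 1, k = 1, ρ = 1): 1/μ + k = 2, which becomes 1 + 1 × (1 − 1/2) = 1.5. The SE goes from √(2 × 2/180) = 0.149 to √(2 × 1.5/180) = 0.129, or 13.4% narrower.

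Example, rare outcome (μ = 0.1, k = 4, ρ = 1): 14 becomes 10 + 4 × (1 − 0.4/1.4) = 12.86. The SE goes from 0.394 to 0.378, or 4.2% narrower.

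Narrowing of the interval on the log scale, over k = 1 to 4:

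| μ | ρ = 1 | ρ = 0.5 |
|---|---|---|
| 0.05 | 0.1-1.4% | 0.0-0.3% |
| 0.1 | 0.4-4.2% | 0.1-1.0% |
| 0.2 | 1.4-10.4% | 0.3-2.5% |
| 0.5 | 5.7-25.5% | 1.4-5.7% |
| 1 | 13.4-40.0% | 3.2-8.3% |
| 2 | 25.5-54.2% | 5.7-10.4% |

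With rare events the 1/μ term dominates and most prior counts are zero, so there is little for the covariate to explain.

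**4. Check by simulation.** Settings: 180 per arm, rate ratio 0.75, full persistence, 400 runs each, negative binomial model with robust SE, with and without the log of the prior count (plus 1/k).

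| μ, k | Formula | Simulated mean SE |
|---|---|---|
| 0.1, 2 | 1.4% | 0.7% |
| 0.2, 2 | 4.2% | 1.7% |
| 0.5, 2 | 13.4% | 8.0% |
| 1, 2 | 25.5% | 18.1% |
| 2, 1 | 25.5% | 20.7% |

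The pattern is the same, but the formula is somewhat optimistic. A separate simulation used 225 per arm, log-normal frailty, log(1 + prior count) and means of 0.3 to 1. Its variance ratios were 0.98 at a pre/post correlation of 0.16, 0.93 at 0.31, 0.83 at 0.48 and 0.69 at 0.65. Taking 1 − √ratio, that is about 1%, 3.6%, 9% and 17% in width.

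**The case against.** Three stronger readings are tempting, and the documents support none of them.

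- *A reader might infer that the T1 EHR data are collected and never used.* The imbalance rule in Section 9.6 is not limited to Aim 1 and offers both a statistical and a clinical route in. Hypothesis 3 uses baseline opioid prescribing, and opioid prescriptions are also an Aim 2 outcome. What remains is that the Aim 2 opioid count model itself names no baseline term, and that imaging, injections, surgery, emergency visits and hospitalisations have no planned analysis that uses baseline.
- *A reader might infer that rare outcomes lose most.* The table above shows the reverse.
- *A reader might infer that the arm comparison is biased, or that a few heavy users could distort it.* Randomisation protects the comparison, the negative binomial allows for overdispersion, and a visible excess of prior heavy users in one arm is what the imbalance rule is meant to catch.

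It is also fair to say that the Table 2 row is damaged, that a look-back window might sit in the data transfer specifications which Section 10.2 says will be developed, and that the window length and the log form are choices on which statisticians may differ. These points limit how firmly the missing window can be criticised. They do not remove the core: the first mark is under T1, and nothing in the documents makes the baseline count a planned covariate for Aim 2.

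**Conclusion.** The point holds as a matter of precision in a secondary aim. The Aim 2 models do not pre-specify the same-outcome baseline count, and the only way in depends on observed imbalance, so adjustment follows chance and may differ across outcomes. On the assumed rates the loss is negligible to small for outcomes such as surgery or hospitalisation if they occur at 0.05-0.1 per patient. It becomes material for commoner use that persists within patients, of which opioid prescriptions are the likeliest case. The top of the full-persistence range is a ceiling, since the simulations gained less than the formula. All sizes rest on assumed event rates, dispersion and persistence, on equal windows, and on ignoring class clustering. The validity of the Aim 2 tests is not in question.

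**What to change.** - **Table 2:** define the T1 EHR value as the count over a fixed period before randomisation (for example 12 months), the same for every outcome and site.
- **Section 9.6, Aim 2:** state that each GEE model will include log(1 + that count) of the same outcome as a fixed covariate, irrespective of observed imbalance.
- **Sparse outcomes:** state a fallback (a yes/no indicator of prior use, or no adjustment) and set its threshold in advance on counts pooled over arms, while blinded.
- **Incomplete look-back:** Section 4.2 asks patients to plan to stay with the clinic for 12 months but sets no prior registration period, so some will have a short history. Add an indicator for incomplete look-back.

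The cost is about a sentence of text and a start date in the extract, with no patient contact. Identifiers already held at each site "will be used to link and extract clinical data from each center’s EHR on a bi-weekly basis". That section does not say how far back the extracts reach, so each site should confirm that the chosen window is available.

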10. DATA COLLECTION AND QUALITY ASSURANCE

10.1 Data Collection

Paperless Data Entry: A paperless data-entry system will be created in REDCap, a secure web application for building and managing online surveys and databases available to the PI ([name]) through the Boston University Clinical and Translational Science Institute. REDCap has proven to be a sophisticated yet easy-to-use data entry system that provides customizable templates for use in clinical trial research. All study participants will be assigned unique study identifiers that will appear on all data collection instruments, documents, and files used in the statistical analysis and manuscript preparation. REDCap allows for specific data quality measures to be implemented. These include data verification and built-in data validation mechanisms such as logic and out of range data checks.

10.2 Data Management

EHR Data: Consenting and eligible participants will provide contact information containing protected health information (PHI) to each HCS’s research staff. PHI will be stored separately from clinical data in a password protected electronic file and will be used to link and extract clinical data from each center’s EHR on a bi-weekly basis. Limited use datasets will be created

at each HCS and will contain a unique study identifier and clinical data including date of birth and visit dates; name, address, social security number and medical record number information will be removed. Limited use datasets will be transferred to the central data repository housed at Boston University Biostatistics and Epidemiology Data Analytics Center (BEDAC). The BEDAC is supported by the Boston University Medical Campus (BUMC) Information Systems and Technology group (IS&T). Data will reside on virtual machines stored inside the BUMC IS&T premium secure environment. Under IS&T, project database access is configured to require encrypted connections, databases are encrypted at rest (AES-256), and all actions to the database are logged. Database transfer will be electronically encrypted via IPsec tunnel or secure socket layering (SSL) encryption technology so that only the intended recipient can decode the data. Applications and databases will be protected by network firewalls that restrict access to designated users and hosts. Restriction and permissions to update the database and to share the database will be controlled by the BEDAC based on staff user role. The BEDAC data manager will develop data transfer specifications and work with each HCS to obtain data through the secure BEDAC portal. The limited use EHR data will be cleaned, aggregated and merged with study data for subsequent analysis.

Missing data: We do not expect substantial missing data due to it being directly entered into the electronic data collection system, which we have used previously. This system has many safeguards such as prohibiting closure of a page if a question has not been answered or the answer is out of range. For instruments with several questions we will use the approach recommended by their authors for calculating total scores and composites when values for an item are missing.

Compliance: We will estimate compliance by the number of sessions attended and estimate the Proportion of participants with various levels of compliance. We will also calculate the proportion of participants missing each session to describe the pattern of compliance.

Dropout analyses: Participants informing us they no longer want to continue in the study will be considered dropouts, and we will look at when these events occur. Dropout rates will be calculated as proportions of participants randomized, and as a cumulative probability of remaining in the study, using survival analysis techniques such as the product-limit estimator. Unlike proportions, the latter statistics, which can be estimated at various times following randomization, take into account when dropouts occur. The information contained in these descriptive analyses may help us to devise strategies for keeping people in the study.

